9.1.1 TCGA Molecular Subtype Analysis

Whole transcriptome sequencing (RNA-seq) data will be aligned to Human Genome Reference Consortium Human Build 38 (GRCh38) using HISAT2⁶³ with Ensembl genes for Homo sapiens version 90 and TCONs. Novel transcripts will be assembled and all gene expression levels (Fragments Per Kilobase per Million fragments, or FPKM) will be calculated using Cufflinks⁶⁴. Read counts will be calculated using featureCounts⁶⁵. Whole exome sequencing data will be aligned to GRCh38 using BWA⁶⁶. Single nucleotide variants will be called using GATK 6 and VarScan2⁶⁷. Small indels and structural variations will be discovered using Pindel⁶⁸. Copy number variations will be analyzed using GISTIC2⁶⁹. RNA-seq data will also be aligned to reference Epstein-Barr Virus (EBV) genes using BLAT⁷⁰. Samples will be classified into subtypes using the methods as described previously³⁸. Pearson's chi-squared test (χ 2) will be applied to TCGA molecular subtypes to evaluate the difference in post-treatment data compared to TCGA data.

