2.2.4 Correlative Studies Background

With more effective chemotherapy and radiation treatment delivery it is increasingly important to identify molecular subtypes that may require dose escalated or targeted therapy. The traditional Lauren classification²⁶ and World Health Organization²⁷ systems categorize gastric tumors by histology and have had limited utility in guiding oncologic therapies or targeted drug discovery. Currently, the only clinically meaningful molecular biomarker is Her2/neu overexpression, with the TOGA trial demonstrating an OS advantage in Her2/neu positive gastric cancer patients treated with trastuzumab plus chemotherapy versus chemotherapy alone²⁸. Unfortunately, only 6-20% of gastric adenocarcinomas demonstrate Her2 overexpression and/or amplification²⁹. Other attempts to classify gastric tumors via microarray and whole transcriptome sequencing were limited by small sample sizes, no associated clinical outcomes, and the use of immortalized cell lines instead of original patient pathology^{30–33}. In contrast to the parallel technologies that guide the management of breast^{34,35} or prostate cancer^{36,37}, there are no clinically implemented biomarker panels or strata that predict or prognosticate outcomes for gastric cancer.

TCGA performed a multiple platform analysis of 295 treatment naïve gastric cancer samples using array-based somatic copy number analysis, whole-exome sequencing, array-based DNA methylation profiling, messenger RNA sequencing,

microRNA sequencing and reverse-phase protein array. They proposed a four molecular subgroup classification system (Figure 1)³⁸. However, the study was performed on treatment naïve tissue, with the potential for high molecular heterogeneity inherent to gastric cancer³⁹. Due to the sample size that was likely restricted by the high cost of multiple platform genomic analysis, it is possible that the heterogeneous cellular makeup of the gastric tumors deterred the detection of consistently differentially expressed biomarkers in the study. Data in esophageal adenocarcinoma indicate that

[figure not shown]

Figure 1. TCGA molecular subtypes of gastric adenocarcinoma. EBV, Epstein-Barr virus; MSI, microsatellite instability; SCNA, somatic copy-number aberrations.

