9.0 CORRELATIVE STUDIES

9.1 Tissue for Research

Patients with pCR will have normal gastric tissue collected at the time of surgery. Fresh tissue will be formalin-fixed and paraffin-embedded (FFPE) per institutional standards.

RNA and whole exome sequencing will be used for formalin-fixed, paraffin-embedded, post-treatment gastric adenocarcinoma tissue samples to determine the post-treatment patient distribution amongst the TCGA molecular subgroups. Blocks will be reviewed by institutional pathologists, H&E slide prepared to identify the block with highest tumor volume and grade (ideally tumor samples with $\geq 60\%$ tumor nuclei and $\leq 20\%$ necrosis will be processed for nucleic acid extraction³⁸) and then the corresponding block sent for biomarker analysis. Normal tissue adjacent to tumor will also be obtained for differential expression analysis. FFPE tissue will be packaged in insulated Styrofoam packaging and shipped to and sequencing performed at the Washington University Genome Technology Access Center. Cold packs and dry ice are not necessary for FFPE tissue samples. Shipping address is:

Genome Technology Access Center [name]

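### The planned chi-squared comparison of subtypes with TCGA changes labeling method and treatment status together, so it cannot separate the two if the labeling methods differ

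*Combined protocol and SAP*

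**What the plan says.** **Comparator.** Section 2.2.4 says "TCGA performed a multiple platform analysis of 295 treatment naïve gastric cancer samples". The platforms are "array-based somatic copy number analysis, whole-exome sequencing, array-based DNA methylation profiling, messenger RNA sequencing", then "microRNA sequencing and reverse-phase protein array", which makes six. From this work, "They proposed a four molecular subgroup classification system".

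**Trial assay.** Section 9.1 says "RNA and whole exome sequencing will be used for formalin-fixed, paraffin-embedded, post-treatment gastric adenocarcinoma tissue samples". Blocks are chosen for high tumor volume and grade, with a preferred minimum of 60% tumor nuclei and maximum of 20% necrosis; the TCGA paper is cited for this.

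**Labeling.** Section 9.1.1 uses BLAT for Epstein-Barr virus alignment, GISTIC2 for copy number, and named tools for variants and indels. For the subtype call it says only "Samples will be classified into subtypes using the methods as described previously", again citing the TCGA paper.

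**Test.** Section 9.1.1 applies Pearson's chi-squared test "to evaluate the difference in post-treatment data compared to TCGA data". It states no significance level.

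**Purpose.** The exploratory objective in Section 3.0 is to determine the subtype distribution after treatment, and the endpoint is the percentage in each subtype. The justification column adds that treatment may favor a different mix of subtypes.

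**The concern.** The two sides of the chi-squared table differ in at least two ways at once. One side is treated and the other is not. One side is labeled from two assays and the other comes from a six-platform analysis. The plan has nothing that would separate these:

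- no written two-assay classification rule;
- no check of how well two-assay labels agree with the published ones;
- no relabeling of TCGA samples by the trial's method;
- no sequencing of pre-treatment tumor in the trial's own patients.

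The stated reason for the endpoint is possible selection by treatment, so a significant result would naturally be read that way. A labeling difference could produce the same result. At stake is the interpretation of one exploratory comparison, which might be carried into later biomarker work.

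**Working it through.** **1. The passages side by side**

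| | TCGA comparator (2.2.4) | Trial (9.1, 9.1.1) |
|---|---|---|
| Tumors | 295, treatment-naive | Residual tumor at surgery, after radiation and chemotherapy |
| Platforms | Six | Two: RNA and exome sequencing |
| Copy number | Array | GISTIC2, with no array planned |
| DNA methylation | Array | Not planned |
| Tissue preservation | Not stated | Formalin-fixed, paraffin-embedded |

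Both trial assays are of kinds listed for TCGA (exome and mRNA sequencing). That is what makes a bridging step possible.

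**2. Number of trial tumors**

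The documents give no sample size for this comparison. Enrollment is 36 and the hypothesized pCR rate is 20% (Section 14.1). Patients with pCR have no residual tumor to classify, so at the hypothesized rate about 36 × (1 − 0.20) = 28.8, or 29, remain. Patients without surgery and unusable blocks reduce this. A range of 20 to 28 is used below as an assumption.

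**3. Illustration of the size**

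There is no plan figure to reproduce. The assumptions are: a 5% test, four subtypes, 295 TCGA tumors against n trial tumors, and identical true shares p₁ to p₄ on both sides. A fraction m of the fourth (largest) subtype is called as the third in the trial only. The documents give neither the shares nor m.

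One-way miscalling gives trial shares

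q₃ = p₃ + m·p₄ and q₄ = (1 − m)·p₄.

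Two-way miscalling at equal rates gives

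q₃ = (1 − m)·p₃ + m·p₄ and q₄ = (1 − m)·p₄ + m·p₃.

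Example with shares 10/20/20/50 and m = 0.30:

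- one-way: q₃ = 0.20 + 0.30 × 0.50 = 0.35 and q₄ = 0.70 × 0.50 = 0.35;
- two-way: q₃ = 0.70 × 0.20 + 0.30 × 0.50 = 0.29 and q₄ = 0.70 × 0.50 + 0.30 × 0.20 = 0.41.

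Rejection rates from simulated 2 × 4 tables, over n = 20 to 28 (40,000 tables per setting):

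| Assumed shares (%) | m | One-way | Two-way |
|---|---|---|---|
| 10/20/20/50 | 0 | about 5% | about 5% |
| 10/20/20/50 | 0.15 | 11–13% | 7–8% |
| 10/20/20/50 | 0.30 | 29–36% | 14–16% |
| 10/25/30/35 | 0 | about 5% | about 5% |
| 10/25/30/35 | 0.15 | 7% | about 5% |
| 10/25/30/35 | 0.30 | 13–16% | about 5% |

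The test holds its level when both sides are labeled alike. Inflation needs net movement from one subtype to another. When the two affected subtypes are of similar size and the errors are symmetric, it nearly disappears.

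**The case against.** The strongest case on the other side has four parts.

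- **A reader might infer that the trial cannot apply the TCGA method at all.** The documents do not support this. Section 2.2.4 says that six platforms fed the analysis behind the four groups. It does not say that assigning one tumor needs all six, and the assignment rule is in a paper not reproduced here. The Figure 1 caption names Epstein-Barr virus, microsatellite instability and copy-number aberrations. Section 9.1.1 plans virus alignment, copy number, and variant and indel calling. It names no microsatellite-instability caller and does not state the rule.
- **A reader might infer that treated blocks have lower tumor purity.** The documents do not show it. Section 9.1 sets tumor-content targets tied to the TCGA paper, although as a preference and not a requirement. Section 11.0 defines partial response as under 10% viable tumor, so specimens with little tumor are foreseeable, but how many would be sequenced is unknown.
- **A reader might infer that the trial will report a labeling difference as a treatment effect.** The objective and endpoint are descriptive, and Section 9.1.1 claims no cause. Only the justification column mentions selection, and as a possibility.
- **The inflation depends on assumed shares and on asymmetric errors.** This is correct, and the two-way column shows it.

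What remains is narrower: the plan tests one set of labels against the other without establishing that they are comparable.

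**Conclusion.** The point holds in conditional form. If two-assay labels on treated tissue differ systematically from the published TCGA labels, the chi-squared test in Section 9.1.1 cannot separate that from an effect of treatment. The documents establish the mismatch and the missing bridge. They do not establish that the labels actually differ.

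The size is illustrative: about 7–36% rejection under one-way miscalls of 15–30%, and about 5–16% under two-way miscalls, against a nominal 5%. These figures rest on two assumed sets of subtype shares, assumed miscall rates, an assumed 5% level and 20 to 28 classified tumors. The upper end is the most unfavorable setting examined, not an expected error rate.

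TCGA's case mix may also differ, since Sections 4.1 and 4.2 limit stage and site and Section 9.1.1 sets no matching restriction. The documents do not give TCGA's stage or site, so this is unverified. The endpoint is exploratory, so this is a low-cost improvement and not a threat to the trial's main result.

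**What to change.** In Section 9.1.1:

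1. State the rule that assigns a subtype from RNA and exome data alone.
2. Apply the same rule to TCGA's own mRNA and exome data, report agreement with the published labels, and use the re-derived labels as the comparator.
3. Add a sensitivity comparison restricted to the stage and site in Section 4.1, where case-level TCGA data allow.
4. Report how many trial tumors could not be classified, by pathologic response.
5. State that a remaining difference may reflect purity, preservation, case mix or the absence of pCR tumors, and is not by itself evidence of a treatment effect.

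The second step removes the difference in platform only; the fifth is needed because the other differences remain.

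The cost is added bioinformatics work, dependence on access to TCGA sequence data, and a smaller comparator in the restricted analysis. No patient procedure or sample-size change is needed.

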9.1.2 Differential Biomarker Expression Analysis

Whole transcriptome sequencing data will be pre-processed excluding genes with consistent low expression levels (e.g. <1 FPKM or <200 reads) across all samples⁷¹. MicroRNA and non-coding small RNA expression will be calculated⁷². The Bioconductor packages including DEseq⁷⁴ and edgeR⁷⁵ will be applied to the above raw read counts in the unit of genes or pathways. Raw read counts are modeled on the negative binomial (NB) distribution in both packages. This is recommended for proper RNA-seq DE analysis since it will handle the well-known over-dispersion

problem by adjusting relevant variables and solving the multiple testing issue. The ratio of means (e.g. log fold-change > 1.5) will be used as the effect size measure as indicated previously⁷⁶, and adjusted false discovery rate (FDR) will be applied to reduce type I errors from a list of differentially expressed genes. All biomarkers discovered will be examined for their predictive and prognostic utility using Kaplan–Meier estimator. Further experiments will include larger discovery and validation patient cohorts using these biomarker panels to verify their association with clinical outcomes in Korean and Western gastric cancer patients⁷⁷.

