2.3 Study Design

2.3.1 Overall Design

The hypothesis of this study is that adaptive SCRT followed by multiagent chemotherapy will result in a pCR of at least 20%.

Thirty-six patients with gastric adenocarcinoma will be enrolled in this study. There will be a lead-in cohort of 5-10 patients (see Safety Cohort and Early Stopping Rules) to ensure there are no grade 5 toxicities related to adaptive SCRT (or SOC chemotherapy after adaptive SCRT). All patients will receive radiation delivered with MR or CBCT guidance followed by sequential chemotherapy. Gastrectomy will occur 2-4 weeks after the completion of chemotherapy. Pathologic response, plan dosimetry, and oncologic outcomes will be evaluated. FDG PET/CTs are strongly encouraged at baseline but optional. Patients will be followed on study for 12 months after surgery.

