14.0 STATISTICAL CONSIDERATIONS

14.1 Statistical Hypotheses and Sample Size Determination

Chemotherapy alone has a pCR rate of 6-16%¹⁰. PCR is defined as a pathologic complete response (no tumor on gastrectomy specimen). We hypothesized that preoperative radiation followed by chemotherapy would result in a pCR rate of 20%, and with 36 patients, our confidence interval for this estimate will fall between 9% and 37%.

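### Section 9.1.2 relates expression biomarkers to outcome by Kaplan-Meier alone, which forces each marker into groups; a continuous Cox analysis would be a cheap, minor improvement

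*Combined protocol and SAP*

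**What the plan says.** Section 9.1.1 puts the markers on a quantitative scale: "all gene expression levels (Fragments Per Kilobase per Million fragments, or FPKM) will be calculated using Cufflinks". Section 9.1.2 then tests for differential expression with two count-based packages: "Raw read counts are modeled on the negative binomial (NB) distribution in both packages". It sets a fold-change threshold and a false-discovery-rate (FDR) adjustment for the resulting gene list.

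For the step from biomarker to patient outcome, Section 9.1.2 has a single sentence: "All biomarkers discovered will be examined for their predictive and prognostic utility using Kaplan–Meier estimator". It gives no cutpoint, grouping rule, regression model, test or significance level, and it does not say which outcome is meant. Section 14 does not fill the gap: Section 14.3 uses Kaplan-Meier only to describe 1-year disease-free and overall survival in the whole group.

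On the number of tumors, Section 2.3.1 says: "Thirty-six patients with gastric adenocarcinoma will be enrolled in this study". Section 9.1 says what is sequenced: "RNA and whole exome sequencing will be used for formalin-fixed, paraffin-embedded, post-treatment gastric adenocarcinoma tissue samples". Section 14.1 defines pCR as absence of tumor on the specimen, so a patient with pCR has no residual tumor to sequence. Section 6.6 says inevaluable patients are not replaced.

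**The concern.** Kaplan-Meier estimates one survival curve per group. To use it with an expression level, the analyst must first turn that level into categories such as high and low. Every patient in a category is then treated alike, and differences within the category are lost. Cutting can be justified by a validated threshold, but these markers are newly discovered and the documents cite none.

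What is at stake is sensitivity. With about thirty tumors or fewer and 12 months of follow-up after surgery, events will be few, and a marker with a graded relation to outcome is easier to miss once it has been split. The open cutpoint also leaves the analyst free to choose a different grouping for each marker.

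**Working it through.** **The plan's own figure.** The only sample-size figure is in Section 14.1: a 20% pCR rate in 36 patients, with an interval of 9% to 37%. A Clopper-Pearson interval at 0.20 x 36 = 7.2 responders gives 8.6% to 36.7%, which agrees after rounding. The documents give no power, effect size or event count for the biomarker analysis, so what follows is a scenario calculation.

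**Number of tumors.** At 20% pCR with every patient resected: 36 x (1 - 0.20) = 28.8, about 29. At the other rates in Section 14.1:
- 6% pCR: 36 x 0.94 = 33.8, about 34
- 16% pCR: 36 x 0.84 = 30.2, about 30
- 37% pCR: 36 x 0.63 = 22.7, about 23

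Patients not resected and unusable blocks would lower these counts. The range 22 to 34 is used below.

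**Information kept by a split.** For a normal marker cut at quantile q, the share kept is phi(z_q)^2 / [q(1 - q)], where phi is the normal density. At the median this is 0.3989^2 / 0.25 = 0.637 = 2/pi. So 29 tumors act like 29 x 0.637 = 18.5. A cut at the 25th or 75th percentile keeps 54%.

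**Large-sample power.** With D events and two-sided 5%:
- continuous marker: Phi(sqrt(D) x ln HR - 1.96)
- median split: Phi(sqrt(2D/pi) x ln HR - 1.96)

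Example: 29 tumors with 35% events gives D = 10.15. At HR 2.0 per SD (ln HR = 0.693):
- continuous: 3.186 x 0.693 - 1.96 = 0.248, power 60%
- split: 2.542 x 0.693 - 1.96 = -0.198, power 42%

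**Simulation.** Because events are few, the comparison was also simulated: normal log expression, exponential times, administrative censoring, and a Cox score test on the continuous marker against a log-rank test on a median split. There were 6,000 trials per cell for 22 and 29 tumors and 8,000 for 34. Entries are power in %, continuous to split, with the loss in points.

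| Tumors | Events | HR 1.5 | HR 2.0 | HR 2.5 |
|---|---|---|---|---|
| 22 | 25% | 15.5 to 9.8 (5.7) | 33.0 to 18.3 (14.7) | 48.8 to 29.2 (19.6) |
| 22 | 35% | 19.8 to 13.3 (6.5) | 43.8 to 25.4 (18.4) | 62.6 to 39.8 (22.8) |
| 22 | 50% | 25.7 to 17.0 (8.7) | 55.9 to 36.4 (19.5) | 77.0 to 53.1 (23.9) |
| 29 | 25% | 18.2 to 12.4 (5.8) | 41.1 to 25.2 (15.9) | 61.5 to 38.9 (22.6) |
| 29 | 35% | 24.6 to 16.5 (8.1) | 55.1 to 35.3 (19.8) | 75.6 to 52.3 (23.3) |
| 29 | 50% | 32.2 to 22.5 (9.7) | 69.7 to 48.3 (21.4) | 87.1 to 66.9 (20.2) |
| 34 | 30% | 25 to 16 (8.4) | 55 to 35 (19.4) | 76 to 52 (23.9) |
| 34 | 50% | 36 to 24 (11.5) | 77 to 55 (22.2) | 92 to 74 (18.7) |

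Repeat runs agreed to within about a point, giving an overall range of roughly 6 to 25. Both tests rejected close to 5% of the time under the null.

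**Outside that grid.**
- At HR 1.25 per SD the loss is 2 to 4 points.
- If the true effect is a step at the median (29 tumors, 35% events, HR 3 between halves), the split is slightly better: 30% against 26%.
- At a per-marker alpha of 0.005 (29 tumors, 35% events), power is 5.5% against 3.3% at HR 1.5, and about 21% against 11% at HR 2.0.

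**The case against.** The strongest reply is that the power figures compare against a test the plan does not name. Kaplan-Meier is an estimator. The log-rank test, the 5% level, the median cut, the hazard ratios and the event rates are all supplied here, and the simulated data follow the log-linear model that Cox regression fits. This stands: the 6 to 25 points are a scenario range, not a measured cost of the plan. It does not remove the need to group, because Kaplan-Meier is the only outcome method named for these markers.

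A second reply is that group-wise curves suit the interest in molecular subgroups (Section 2.2.4) and in panels (Section 9.1.2). That supports keeping the curves as a display. It does not support making them the only analysis of a quantitative marker.

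Three stronger readings are tempting, and the documents do not support them:
- **The Kaplan-Meier step decides which markers go forward.** Section 9.1.2 finds markers by differential expression and then examines them against outcome. It mentions larger later cohorts to verify the associations, but states no threshold or selection rule based on the curves.
- **Twenty-nine tumors is a maximum.** It is the number expected at 20% pCR with all patients resected. At 6% pCR about 34 would remain, although the loss hardly changes.
- **False positives are inflated.** Searching for the best cut between the 20th and 80th percentiles would give about 26-28% false positives instead of 5%, but the plan does not propose such a search. It only fails to rule one out.

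**Conclusion.** The point holds as a minor improvement. As written, Section 9.1.2 needs every expression marker to be grouped, cites no validated cutpoint, and names no analysis that keeps the marker continuous. A median split of a normal marker gives up about 36% of the information (100% - 64%). If effects are log-linear with HR 1.5 to 2.5 per SD, that is roughly 6 to 25 points of power at two-sided 5% per marker. Weak effects lose little, a true step at the median slightly reverses the comparison, and under strict multiplicity control both methods have low power.

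Section 3.0 lists the biomarker objective as exploratory, and its endpoint is the markers themselves rather than a survival association. The pCR result, the secondary endpoints and the safety rules are untouched.

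**What to change.** In Section 9.1.2, replace the Kaplan-Meier sentence with wording such as: *The association of each discovered biomarker with outcome will be estimated by Cox regression with log-transformed normalized expression as a continuous covariate, reporting the hazard ratio per SD with 95% confidence interval and FDR-adjusted p-value. Kaplan-Meier curves split at the median will be shown for display only.* The same sentence should name the outcome, which the section leaves open.

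The cost is one sentence and a few lines of code, with no new patients, samples or visits. The change also settles the cutpoint in advance and extends the FDR adjustment, now stated only for the differential-expression list, to the outcome step. The downside is an assumption of log-linearity, which should be checked with residual plots, although a check on so few events will be rough.
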